5.3 Used dosage of UC-MSC

The amount of UC-MSC was calculated according to 0.5×10^6 UC-MSC/kg body weight. UC-MSC were infused intravenously three times at 4-week intervals.

5.4 Treatment method and course of treatment

UC-MSC was suspended in 200 mL of saline and infused intravenously into the patient's forearm.

5.5 Conventional clinical treatment

Antiviral therapy in accordance with *the Guidelines for the prevention and treatment of chronic hepatitis B: APASL (2008 edition).*

The treatment of ascites, peritonitis, hepatorenal syndrome, and upper gastrointestinal bleeding was performed in accordance with the current domestic clinical routine treatment program.

6 Research process

All subjects are required to sign an informed consent form before screening. This study was divided into a screening period, a treatment period, and a follow-up period. The treatment period was 8 weeks and the follow-up period comprised about 73 months. Screening period: $-7\sim0$ days, treatment period: Week 0 (baseline), week 4, week 8; Follow-up periods: 2 weeks, 12 weeks, 24 weeks, 48 weeks, 24 months, 48 months, 60 months, and 75 months (see table 4). The specific visit items are as follows:

6. 1 Follow-up process

Table 4 Follow-up flow chart

	Screenin		On treatment & Posttreatment visit period										
Visit item	g period	Treatment 1	Visit 1	Treatment 2	Treatment 3	Visit 2	Visit 3	Visit 4	Visit 5	Visit 6	Visit 7	Visit 8	
Visit time	-7~0 Day	Week 0	Week 2 ±2 days	Week 4 ±2 days	Week 8 ±7 days	Week 12 ±7 days	Week 24 ±14 days	Week 48 ±14 days	Month 24 ±15 days	Month 48 ±15 days	Month 60 ±30 days	Month 75 ±30 days	
Informed consent	×												
Demographics	×												
Medical history	×												
Weight	×	×	×	×	×	×	×	×					
Vital signs	×	×	×	×	×	×	×	×					
Physical examination	×	×	×	×	×	×	×	×					
Urine pregnancy test (female)	×		×		×	×	×						
Routine blood test	×		×	×	×	×	×	×					

	Screenin		On treatment & Posttreatment visit period										
Visit item	g period	Treatment 1	Visit 1	Treatment 2	Treatment 3	Visit 2	Visit 3	Visit 4	Visit 5	Visit 6	Visit 7	Visit 8	
Visit time	−7~0 Day	Week 0	Week 2 ±2 days	Week 4 ±2 days	Week 8 ±7 days	Week 12 ±7 days	Week 24 ±14 days	Week 48 ±14 days	Month 24 ±15 days	Month 48 ±15 days	Month 60 ±30 days	Month 75 ±30 days	
Routine urine test	×		×	×	×	×	×	×					
Biochemical test	×		×	×	×	×	×	×					
Coagulation function	×		×	×	×	×	×	×					
HbA1c	×												
Five items of hepatitis B	×												
HBV DNA	×					×	×	×					
AFP	×					×	×	×					
Anti-HCV	×												
Anti-HIV	×												
Abdominal ultrasound	×					×	×	×					

Visit item	Screenin g period	On treatment & Posttreatment visit period										
		Treatment 1	Visit 1	Treatment 2	Treatment 3	Visit 2	Visit 3	Visit 4	Visit 5	Visit 6	Visit 7	Visit 8
Visit time	-7~0 Day	Week 0	Week 2 ±2 days	Week 4 ±2 days	Week 8 ±7 days	Week 12 ±7 days	Week 24 ±14 days	Week 48 ±14 days	Month 24 ±15 days	Month 48 ±15 days	Month 60 \pm 30 days	Month 75 \pm 30 days
Chest X-ray	×											
Electrocardio gram (ECG)	×											
Adverse events (AEs)			×	×	×	×	×	×				
Complications			×	×	×	×	×	×				
UC-MSC infusion		×		×	×							
survival status (follow-up by telephone)									×	×	×	×
Occurrence HCC (follow-up by telephone)									×	×	×	×

6.2 Screening period: (-7~0 days)

(1) Signing of the informed consent form

The investigator or subinvestigator will fully explain the nature of the study to a subject using the institutional review board (IRB)-approved informed consent document. If the subject agrees to participate in the study, the subject must voluntarily sign an informed consent form before the initiation of any study procedures. A copy of the signed and dated informed consent document will be given to the subject. The signed and dated original consent form will be retained by the investigator. Informed consent must be obtained from all subjects. A subject cannot be entered into the study until he or she has signed and dated on the consent form. The investigator or subinvestigator is responsible for ensuring that the subject understands the risks and benefits of participating in the study and should answer any questions the subject may have during the discussion of informed consent performed before study initiation, as well as during the study period. The investigator or subinvestigator is also responsible for sharing any new information in a timely manner that might affect the subject's willingness to continue his or her participation in the study.

(2) Ask for demographic information and past medical history

The following baseline subject characteristics will be obtained and entered in the CRF: Date of written informed consent by the subject, date of birth, sex, ethnicity, race, inpatient or outpatient status, smoking habit, drinking habit, prior therapy, and medical history. Medical history will include any previous medical condition requiring hospitalization, all concurrent medical conditions, surgical history (within 12 months), time of influenza vaccination (within 12 months), diagnosis of influenza virus infection, and time of onset.

(3) Weight measurement

Weight measurement will be performed before treatment and during each visit, in accordance with the requirements of the study process. The weight test will be performed by the researchers.

(4) Physical examination and vital signs

Physical examination (see table 5) and vital signs (see tables 5 and 6) will be performed before treatment and during each visit, in accordance with the requirements of the study process. The

physical examination is completed by the researcher and judged by the researcher. Blood sample collection and processing will be performed in accordance with standard operating procedures (Appendix 3)

Physical	T 11 (Testing	
examination	Indicators	organization	
Vit-1 -i	Body temperature (Tm), respiratory (Br), pulse (Pu), blood pressure	202.11	
vital signs	(systolic blood pressure SBP, diastolic blood pressure DBP).	302 Hospital	
Physical	Skin and mucosa, lymph nodes, facial features (head, eyes, ears, nose,	202 Hogrital	
examination	pharynx), neck, chest, abdomen, spine, limbs, and others.	302 Hospital	
Pregnancy	Urinary pregnancy examination.		
examination.		302 Hospital	
(women only)			
	Leukocyte (WBC), percentage of neutrophils (NE%), absolute value of		
	neutrophils (NEU#), percentage of lymphocytes (LY%), absolute value of		
Douting blood	lymphocytes (LYM#), percentage of monocytes (MO%), absolute value of		
tosta	monocytes (MON#), percentage of eosinophils (EO%), absolute value of	302 Hospital	
lests	eosinophils (EO#), percentage of basophils (BA%), absolute value of		
	basophils (BAS#), erythrocyte (RBC), hemoglobin (HGB), and Platelets		
	(PLT)		
	PH (PH), leukocyte (LEU), nitrite (NIT), protein (PRO), glucose (GLU),		
Poutino urino	ketone body (KET), urinary bilirubin (UBG), bilirubin (BIL), erythrocyte		
	(ERY), urinary sediment microscopic examination of leukocytes	302 Hospital	
lesis	(WBC/HP), and microscopic examination of red blood cells (RBC/HP)		
	with urinary sediment.		
Blood	Liver function: Total protein (TP), albumin (ALB), direct bilirubin	302 Hospital	

Table 5 Physical examination item list

biochemistry	(DBIL), total bilirubin (TBIL), alanine aminotransferase (ALT), aspartate					
	aminotransferase (AST), cholinesterase (CHE).					
	Renal function: Urea (UREA), creatinine (CRE).					
	Blood glucose, blood lipid: Glucose (GLU), triglyceride (TG), and total					
	cholesterol (TC).					
Coagulation	Prothrombin time (PT), prothrombin activity (PTA), and international					
function	standardized ratio (INR)	302 Hospital				
Upper	Liver, gallbladder, spleen, pancreas, and kidney					
abdominal	odominal					
ultrasound						
HbA1c	Glycosylated hemoglobin	302 Hospital				
HBV tests	Serum: HBsAg/anti-HBs, HBeAg/anti-HBe, anti-HBcAg	302 Hospital				
HBV DNA	Serum: HBV DNA	302 Hospital				
Alpha	AFP	20211				
fetoprotein	ein					
anti-HCV	Serum: anti-HCV	302 Hospital				
anti-HIV	Serum: anti-HIV	302 Hospital				
Chest X-ray	K-ray Anterior and lateral chest position					
Electrocardiogra	Heart rate (HR), P-R interval, QRS time, QT/ QTc, ECG diagnosis	202 11:1				
m (ECG)		302 Hospital				
Adverse events	Evaluate according to the international NCI-CTC AE v4.0 standard	302 Hospital				
Comuli, ti	Infection, gastrointestinal bleeding, encephalopathy, and hepatorenal	202.11				
Complications	syndrome	502 Hospital				

X7. 1 '	Normal range				
Vital signs	Lower limit	Upper limit			
Body temperature (armpit)	36 °C	37 °C			
Breathing	16 times / min	20 times / min			
Pulse	60 times / min	100 times / min			
Blood pressure (diastolic blood pressure)	60 mmHg	90 mmHg			
Blood pressure (systolic blood pressure)	90 mmHg	140 mmHg			

Table 6. Normal range of vital signs

(5) Pregnancy examination

In this study, women of childbearing age include: Female subjects younger than 50 years of age without menopause; Female subjects with menopause for ≤ 2 years and without surgical sterilization (bilateral tubal rolling, bilateral ovariectomy, or hysterectomy). Female partners who do not undergo surgical sterilization of male subjects are also considered women of childbearing age if they meet the above definition.

During the screening visit, women of childbearing age should be asked whether they have a history of menopause, what kind of contraception they use, and urine pregnancy tests should be carried out to determine whether they are qualified to join the group.

Female subjects of childbearing age should take effective contraceptive measures during the screening period, the treatment period, and within 16 weeks after the end of treatment (interview 5).

a. Time of collection of pregnancy information.

From the beginning of treatment (treatment 1) to 24 weeks (visit 3), information on all pregnancy events (including female partners of male subjects) at this stage should be collected. During each visit, the menstruation of female subjects of childbearing age should be enquired, such as delayed menstruation for 7 days or more, or delayed menstruation and did not take appropriate contraceptive measures (including unprotected sex); a urine pregnancy test should be performed.

Researchers may not actively collect pregnancy events within 16 to 40 weeks after the termination of MSC treatment (visits 3 to 4). If they know of any pregnancy events, they should inform the principal researchers in charge of the clinical study, including by email. Further treatment is carried out in accordance with the requirements of the Medical Ethics Committee and clinical trial institutions of the center.

b. Pregnancy report.

During treatment, once the female subject spontaneously reports or is later found that the female subject was pregnant or is likely to become pregnant, MSC should be discontinued immediately unless the researchers judged that the immediate cessation of MSC infusion would have serious medical consequences.

If any female subject or female partner of a male subject is found to be pregnant during the trial, the researcher should report to the unit responsible for the clinical study within 24 hours of being informed of her pregnancy and fill in the pregnancy report in a timely manner. The pregnancy of the subjects will be followed up until the end of the pregnancy (12 weeks after the due date) or the termination of the pregnancy, and the results will be reported to the unit responsible for the clinical study, which the researchers submitted as a follow-up report to the pregnancy report. Pregnancy events reported or found during the screening period should also be notified in writing (including e-mail) to the unit responsible for the clinical study and further dealt with in accordance with the requirements of the Medical Ethics Committee and the clinical trial institution of the center.

Pregnancy itself does not act as AE or SAE, but any complications during pregnancy (such as spontaneous abortion) or the choice of termination of pregnancy for medical reasons, and visits, will be recorded and followed up in accordance with the provisions of the program, and in accordance with AEs or SAEs. The pregnancy events of the female partners of the male subjects will be reported and followed up with reference to the pregnancy events of the female subjects.

(6) Routine blood tests

The routine blood tests will be completed by the clinical examination center of our hospital. The examination items are shown in Table 5. The results will be judged by the researchers.

(7) Routine urine tests

The urine routine tests will be completed by the clinical examination center of our hospital. The examination items are shown in Table 5. The results will be judged by the researchers.

(8) Coagulation function tests

The coagulation function tests will be completed by the clinical examination center of our hospital. The examination items are shown in Table 5. The results will be judged by the researchers.

(9) Glycosylated hemoglobin

The glycosylated hemoglobin test will be completed by the clinical examination center of our hospital. The results will be judged by the researchers.

(10) HBV tests

The HBV tests will be completed by the clinical examination center of our hospital. The results will be judged by the researchers.

(11) HBV DNA

The HBV DNA test will be completed by the clinical examination center of our hospital. The results will be judged by the researchers.

(12) AFP

The AFP test will be completed by the clinical examination center of our hospital. The results will be judged by the researchers.

(13) anti-HCV

The anti-HCV test will be completed by the clinical examination center of our hospital. The results will be judged by the researchers.

(14) anti-HIV

The anti-HIV test will be completed by the clinical examination center of our hospital. The results will be judged by the researchers.

(15) B-ultrasound examination of upper abdomen.

Professional doctors will provide diagnostic advice, and the results will be judged by the researchers.

(16) Chest X-ray

X-ray examination of anterior and lateral chest. Professional doctors will provide diagnostic advice, and the results will be judged by the researchers.

(17) Electrocardiographic examination

According to the requirements of the study process, a 12-lead ECG examination will be performed before treatment and during each visit. The ECG contents include the heart rate (HR), P-R interval, QRS time, QT/ QTc, ECG diagnosis (see Table 5). Professional doctors will provide diagnostic advice, and the results will be judged by the researchers.

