4.1 Inclusion Criteria

Subjects who meet all of the following conditions will be entered into the trial:

(1) Patients aged from 18 to 65 years.

(2) Testing positive for serum hepatitis B surface antigen (HBsAg) for more than 6 months.

(3) Diagnosis of decompensated liver cirrhosis, which was defined as liver cirrhosis with serious complications, such as ascites, hepatic encephalopathy, and esophageal and gastric variceal hemorrhage, according to Prevention and Treatment of Chronic Hepatitis B (China 2009).

(4) Negative pregnancy test (female patients of fertile age).

(5) Volunteering to participate in this clinical trial, and able to understand and provide signed informed consent.

(6) Patients with hepatitis B infection-related cirrhosis treated with anti-HBV therapy.

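### The childbearing-age definition in section 6.2(5) leaves eligible women of 50 to 65 who still menstruate outside the contraception and menstrual-enquiry duties

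*Protocol*

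**What the plan says.** Protocol section 4.1 sets the age range, "1) Patients aged from 18 to 65 years", and a screening condition, "4) Negative pregnancy test (female patients of fertile age". It does not define fertile age.

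Section 6.2(5) gives two groups of women of childbearing age. The first is "Female subjects younger than 50 years of age without menopause". The second is "Female subjects with menopause for ≤ 2 years and without surgical sterilization". The next sentence extends the term to female partners, who "are also considered women of childbearing age if they meet the above definition".

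Three duties in 6.2(5) are then written for women of childbearing age:

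- Screening: "urine pregnancy tests should be carried out to determine whether they are qualified to join the group".
- Contraception: "Female subjects of childbearing age should take effective contraceptive measures during the screening period, the treatment period, and within 16 weeks after"; this 16-week span starts when treatment ends.
- Enquiry (6.2(5)a): "During each visit, the menstruation of female subjects of childbearing age should be enquired". A urine test follows if menstruation is delayed by 7 days or more, or is delayed without adequate contraception.

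Sections 6.4, 6.6, 6.7 and 6.8 use the same term for the tests at weeks 2, 8, 12 and 24 and tie them to abnormal menstruation. The synopsis visit schedule and Table 4 mark tests at the same four visits for females, with no age limit and no menstrual condition. Section 6.5 and both tables list no pregnancy item at week 4, the day of the second infusion.

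On stopping, section 4.3(3) withdraws a woman who is pregnant during treatment, without exception. Section 6.2(5)b covers a woman who is pregnant or likely to become so. It stops the cells at once unless the researchers judge that stopping at once would do serious medical harm.

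**The concern.** The age limit sits on the group whose fertility is least in doubt, women who have not reached menopause. The group already in menopause has no age limit. Among women over 50, the less fertile therefore carry the precautions and the more fertile do not. That can hardly be intended.

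The stake is participant safety. Pregnancy is an exclusion (4.2(2)) and a withdrawal criterion (4.3(3)), so the rules meant to prevent it and detect it early should cover every eligible woman who could conceive. The rule for what happens once pregnancy is found should also have one meaning, and the exception in 6.2(5)b leaves room for two.

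**Working it through.** No power or error-rate calculation bears on this point. The check sets the rules side by side.

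**1. Is the list a definition?** The verb that introduces it could suggest examples only. However, the sentence on partners relies on it as "are also considered women of childbearing age if they meet the above definition", so the protocol itself treats the two groups as the test.

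**2. Who is covered, among eligible non-sterilised women?**

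| Woman | Group 1 | Group 2 | Covered |
|---|---|---|---|
| Under 50, not menopausal | yes | no | yes |
| Any age, menopausal 2 years or less | no | yes | yes |
| Any age, menopausal more than 2 years | no | no | no, as intended |
| 50 to 65, not menopausal | no (age) | no (menopause not reached) | **no** |

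**3. Which provisions reach the woman in the last row?**

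| Provision | Reaches her? |
|---|---|
| Contraception, 6.2(5) | no |
| Menstrual enquiry and delay-triggered test, 6.2(5)a | no |
| Conditional tests, 6.4 and 6.6 to 6.8 | no |
| Screening test, 6.2(5) | no, but inclusion 4 may require one |
| Table row for females (screening, weeks 2, 8, 12, 24) | yes, on its label |
| Collection of pregnancy events to week 24; 24-hour report | yes, once pregnant |
| Withdrawal, 4.3(3) | yes, once pregnant |

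No provision that reaches her asks for contraception or for a menstrual history. Whether she is tested after screening depends on whether staff follow the tables or the visit text.

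**4. Week 4.** Scheduled visits from week 2 to week 24 fall at weeks 2, 4, 8, 12 and 24. The pregnancy item is listed at 4 of these 5. Week 4 is missing, although 6.2(5)a requires enquiry at each visit.

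**5. Stopping rule.** Infusions are at weeks 0, 4 and 8, and eligibility is verified again at week 0 (6.3). The exception in 6.2(5)b can therefore bear on at most 2 of the 3 infusions, and only in the UC-MSC arm (125 planned). For a confirmed pregnancy, 4.3(3) gives withdrawal in every case. Section 6.2(5)b gives the same result if its exception concerns only how abruptly a running infusion is stopped. It gives a different result if the exception covers the next scheduled infusion. The text does not say which.

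**6. Size.** The protocol gives no sex or menopausal distribution. Purely as an assumption, if 0.5% to 4% of the 250 patients are menstruating women of 50 to 65:

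- 0.005 × 250 = 1.25 and 0.04 × 250 = 10, so about 1 to 10 women.
- At 1:1 allocation, half of them would be in the UC-MSC arm.

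I put no duration on the gap. The sentence that ends the contraception period cites interview 5, whereas Visit 5 in the schedule is at month 24.

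**The case against.** The strongest reply is that other rules limit the gap. Inclusion 4 has no age cap, pregnancy is an exclusion that is checked again at week 0, both tables show tests for females of any age, and withdrawal and reporting do not depend on the definition. This is correct. A reader might infer that these women enter untested and unprotected, and the document does not support that. What remains is narrower: no contraception duty, no menstrual enquiry, and no tests under the visit text.

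On the stopping rule, the reply is that UC-MSC is given as three separate infusions, that the exception speaks of immediate cessation, and that a withdrawn woman has no later infusion. On that reading nothing conflicts with 4.3(3). This also stands as a possible reading. A reader might infer that the protocol plainly permits infusion in pregnancy or contradicts itself. It does neither: the clause is ambiguous, because it is not limited to an infusion already running. The clause also covers women not yet pregnant, whom 4.3(3) does not reach, so judgement has a proper place there.

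The week 4 omission is partly answered by 6.2(5)a, which already requires the enquiry at that visit. It is an inconsistency in the schedule, not a missing duty for women whom the definition covers.

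**Conclusion.** The definition gap holds on the text. Women of 50 to 65 who have not reached menopause are eligible but fall outside the contraception duty, the menstrual enquiry and the visit-text tests. This rests on reading the list in 6.2(5) as a definition, as the protocol itself does.

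The number of women affected is unknown and probably small. The width of the age band is no guide, since the band also holds men and women past menopause. The 1 to 10 women above rest wholly on an assumed share.

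The exception in 6.2(5)b is a secondary point, an ambiguity worth closing. The missing week 4 item is a lesser consistency point. None of this affects the endpoints, the sample size or alpha. It merits correction because the rules concern participant safety and the change costs almost nothing.

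**What to change.** 1. In 6.2(5), delete the age limit from the first group, so that it reads: *Female subjects without menopause*.
2. In 6.2(5)b, state that no further UC-MSC infusion is given once pregnancy is confirmed and that 4.3(3) governs. Keep investigator judgement only for a woman who is not yet pregnant.
3. List the pregnancy item at week 4 in 6.5 and in both tables.

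Do not settle the difference between tables and visit text by making the table row conditional on abnormal menstruation. That would remove the unconditional tests that both tables show for every female at weeks 2, 8, 12 and 24, including those that now reach the women in question. Keep the tables' more protective schedule.

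The cost is amendment wording and an occasional extra urine test at a visit already scheduled. Newly covered women also take on the contraception duty and the menstrual enquiry, which is the purpose of the change.

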6.3 Treatment 1 (week 0) baseline phase

- (I) The verification of inclusion criteria and exclusion criteria should be carried out again;
- (2) Weight measurement;
- (3) Vital signs and physical examination;
- (4) Treatment with UC-MSC.

